3.1 Primary Objective(s)

- 3.1.1 To collect safety data on patients in whom MSOT was used to image tumor or lymph nodes
- 3.1.2 To evaluate skin temperature pre and post imaging (pre- and post-surgery) as part of the safety evaluation of MSOT

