6.0 Study Outcomes and Study Measures

6.1 Primary Outcome

- 6.1.1 Adverse events as characterized by CTCAE v5.0 in patients that may result from MSOT imaging ($\geq 44^{\circ}\text{C}$)¹³
- 6.1.2 Measurement of skin temperature pre- and post-MSOT imaging (pre- and post-surgery 4 measurements total) with a touch thermometer as part of the safety evaluation of the MSOT device. The thermometer will be placed onto the skin until a temperature appears, about 1 minute, and the temperature will be recorded.

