10.0 Statistical Considerations

10.1 Analysis of Primary Objective

10.1.1 The primary objectives are to estimate the rate of adverse events and measure the skin temperature change following MSOT imaging both pre- and post-surgery. The adverse events will be estimated by grade, type and relatedness. The first analysis will pool all grade 3 unexpected events that are possibly, probably or definitely related to MSOT together and then construct a 95% exact Clopper-Pearson binomial confidence interval for this estimate. Additionally, measurement of skin temperature will be evaluated where skin temperature greater than 44°C will be recorded¹³. A 95% exact Clopper-Pearson binomial confidence interval for the evaluation of skin temperature will be conducted

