Appendix A – Imaging and Tissue Data Collection Form

Study Number: OU-SCC-MSOT PID: 0 1 - _____

Investigator: [name] Surgery Date: ____/____/____

1) Tumor or Lymph Node Assessments:

a) Target tissue

Tumor

Lymph Node

b) Standard of care method of imaging

MRI _____ tumor amount

PET _____ tumor amount

CT _____ tumor amount

Other: _____ tumor amount

c) Did patient receive neoadjuvant therapy?

Yes

No

d) MSOT Image acquired?

Yes

No

e) Was an indicator dye used during surgery?

Yes

[figure not shown]
No

f) If an indicator dye used during surgery, please indicate which dye.

Isosulfan Blue IC Green

2) Location of Imaging

a) Please circle the location of the imaging (below) and provide further description as necessary

[https://anatomyclass123.com /](https://anatomyclass123.com/)

b) Erythema post-MSOT Imaging (RTOG)

i. Time after imaging: (hr: min) _____

ii. Grade (RTOG)

- 0 No erythema present
- 1 Follicular, faint or dull erythema, epilation, dry desquamation, decreased sweating
- 2 Tender or bright erythema, patchy moist desquamation, moderate edema
- 3 Confluent, moist desquamations other than skin folds, pitting, edema
- 4 Ulceration, hemorrhage, necrosis

3) Clinical Pathology Assessment

a) Date or diagnosis (month / year):

b) Positive tumor tissue:

Yes No
 c) For Pancreatic melanoma breast HNSCC ovarian (check one) indicate stage at diagnosis (**TNM classification**):

Tx T0 Tis T1 T2 T3 T4
 Nx N0 N1 N2 N3
 Mx M0 M1

d) Tumor subtype (if applicable) _____

4) Skin temperatures

Pre-Surgery MSOT imaging			
Pre-imaging Skin Temperature (°C)		Time	
Post-imaging Skin Temperature (°C)		Time	

Post-Surgery MSOT imaging			
Pre-imaging Skin Temperature (°C)		Time	
Post-imaging Skin Temperature (°C)		Time	

5) Patient Monitoring (*)please note that patients must be monitored daily for adverse events until discharge). Please answer yes or no if Erythema at grade III or higher or change in skin pigmentation occurs.**

Yes No

_____ Post surgery	_____ 8 day
_____ 1 day	_____ 9 day
_____ 2 day	_____ 10 day
_____ 3 day	_____ 11 day
_____ 4 day	_____ 12 day
_____ 5 day	_____ 13 day
_____ 6 day	_____ 14 day
_____ 7 day	_____ 15 day

Discharge date: _____

6) Adverse event. Please answer yes or no if Erythema at grade III or higher or change in skin pigmentation occurs.

Yes No

If yes, please fill out details below:

_____ Erythema _____ Time _____ Date

_____ Changes in skin pigmentation _____ Date

7) MSOT Scan Times:

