- ix. Patients with Stage IV pancreatic cancer, Stage IV HNSCC are not surgical candidates and therefore excluded from this study

5. Analysis Populations

- **Safety population:** All subjects who received MSOT readings will be included in the overall safety analysis, with toxicities graded according to NCI CTCAE v5.0. This is primarily a safety analysis study.

6. Summary of Study Population

a. Patient Disposition

- i. Descriptive statistics on the demographics and presenting features will be calculated. Proportions will be calculated for categorical variables and medians with the minimum and maximum will be calculated for continuous variables.

7. Safety Analyses

a. Adverse Events

- i. The severity of the AE will be graded by the Investigator using the NCI CTCAE, version 5.0.
- ii. The adverse events will be estimated by grade, type and relatedness. The first analysis will pool all grade 3 unexpected events that are possibly, probably or

definitely related to MSOT together and then construct a 95% exact Clopper-Pearson binomial confidence interval for this estimate.

b. Temperature Analysis

- i. Measurement of skin temperature will be evaluated where skin temperature greater than 44°C will be recorded and a 95% exact Clopper-Pearson binomial confidence interval constructed.

c. Secondary Analysis

- i. Tumor positivity from pathology reports and MSOT readings will be compared and Pearson correlation coefficient created.
- ii. Deoxy- and oxy-genation levels will be compared to non-tumor values from the same patient. Paired t-tests will be used to compare the values and a Wilcoxon Signed Rank test performed. Median and interquartile range will be reported.

8. Handling of Missing Data

Every effort will be made to collect information at all defined visits including at early withdrawal or dropout. Reasons for missing data will be summarized. However, there will be no imputation of missing data.

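### Skin-temperature change is a primary objective, but the only planned temperature analysis is a proportion above 44°C, which cannot estimate change

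*Protocol*

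**What the plan says.** The objective and the data collection both concern a before/after comparison:

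- Protocol 3.1.2: "To evaluate skin temperature pre and post imaging (pre- and post-surgery) as part of the safety evaluation of MSOT".
- Protocol 10.1.1, restating the primary objectives for analysis: "measure the skin temperature change following MSOT imaging both pre- and post-surgery".
- Protocol 6.1.2, the outcome: "Measurement of skin temperature pre- and post-MSOT imaging (pre- and post-surgery 4 measurements total". No cut-off is attached to it.
- Appendix A item 4: for each of the pre-surgery and post-surgery sessions, a field for "Pre-imaging Skin Temperature (°C" and a matching post-imaging field, each with a time.

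The planned analysis concerns a threshold:

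- Protocol 10.1.1: "measurement of skin temperature will be evaluated where skin temperature greater than 44°C will be recorded", followed by a 95% exact Clopper-Pearson interval.
- SAP 7.b: "Measurement of skin temperature will be evaluated where skin temperature greater than 44°C will be recorded", again with a Clopper-Pearson interval and nothing further.

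**The concern.** A Clopper-Pearson interval is a method for a proportion. Applied to readings above 44°C, it says how often a limit was passed. It does not say how far skin temperature moved between the two readings of a session. The pairing that 6.1.2 and Appendix A set up is not used.

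Sections 8.1, 8.6 and 10.3.1 of the protocol all name a temperature rise in sensitive skin as the effect to expect from the device. Warming that stays below the cut-off and causes no reportable skin reaction would have no planned estimate. Evident reactions would still be seen through adverse-event monitoring and the RTOG erythema grade in Appendix A item 2b. What would be lost is the size of the temperature change.

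**Working it through.** **Is change analysed anywhere else?** Three other places plan descriptive or paired statistics, and none covers temperature:

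- SAP 6.a: "Descriptive statistics on the demographics and presenting features will be calculated". This covers demographics and presenting features.
- SAP 7.c.ii: paired t-test and Wilcoxon signed-rank test, then "Median and interquartile range will be reported". These compare oxygenation levels in tumour and non-tumour tissue.
- Protocol 10.2: a paired t-test comparing MSOT with standard-of-care tumour volume or size.

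**What the planned analysis can show.** Let a patient's pre-imaging reading be b and the post-imaging reading b + d. If neither reading exceeds 44°C, the patient contributes a zero for every d up to 44 − b. With no exceedances the result depends only on n.

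**Reproducing the plan's figures.** For zero events the upper 95% Clopper-Pearson limit is 1 − 0.025^(1/n).

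- n = 50: 1 − 0.025^(1/50) = 7.11%. Protocol 10.3.1 gives 7.1%.
- n = 45: 1 − 0.025^(1/45) = 7.87%. Protocol 10.3.1 gives 7.9%.

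The protocol states these limits for adverse events; the same method applied to zero exceedances gives the same limits. The n = 45 case matters because 10.3.1 ends the study at 45 patients if 3 or fewer adverse events are seen.

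**What a paired summary would give.** The 95% CI half-width for the mean change in one session, in units of the SD of the change, is t(0.975, n − 1)/√n, where n is the number of patients with both readings in that session.

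- n = 50: 0.284 SD.
- n = 45: 0.300 SD.

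The documents give no SD. For scale only, an assumed SD between 0.5 and 3°C would put the half-width at n = 50 between 0.284 × 0.5 = 0.14°C and 0.284 × 3 = 0.85°C.

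**The unstated unit.** Neither 10.1.1 nor SAP 7.b says whether the temperature interval counts patients or readings. With no exceedances the upper limits are:

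| Unit | 45 patients | 50 patients |
|---|---|---|
| Patient | 0/45: 7.9% | 0/50: 7.1% |
| Post-imaging readings only (2 per patient) | 0/90: 4.0% | 0/100: 3.6% |
| All readings (4 per patient) | 0/180: 2.0% | 0/200: 1.8% |

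The lower two rows treat readings from the same patient as independent. They are correlated, so those intervals are too narrow.

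**The case against.** The strongest reply has four parts.

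1. *Only the opening of 10.1.1 uses the word change.* Objective 3.1.2 asks for an evaluation before and after imaging, and a safety threshold tied to a cited thermal-damage reference is one legitimate evaluation. This is fair as to 3.1.2. It does not remove the mismatch inside 10.1.1, where objective and analysis stand in the same paragraph.
2. *Adverse-event reporting covers warming below 44°C.* Sections 8.1 and 8.6 list temperature rise as an expected effect, mild events are monitored, and events are tabulated by grade, type and relatedness. So warming judged to be an adverse event would be counted. But 8.6 makes expected effects adverse events only when the investigator finds them beyond normal frequency and severity, and the first pooled analysis takes only unexpected grade 3 events. A count also gives no size of change.
3. *No decision depends on it.* The expansion and early-stopping rules use adverse events, the readings are kept, and a table could be made later. With no control arm, skin preparation, gel, anaesthesia and, in the second session, the operation itself may all contribute to the change. This stands and limits the weight of the point. A later table would, however, be an unplanned answer to a primary objective.
4. *The side points are minor.* Sample sizes elsewhere are counted in patients, so patient is the natural reading of the unit; the per-reading figures only show what the silence allows. The at-or-above-44°C wording in 6.1.1 and SAP 2.a.i belongs to the adverse-event outcome, whereas the above-44°C wording in 10.1.1 and SAP 7.b belongs to the temperature analysis. Both points are accepted as matters of wording.

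**Conclusion.** The concern holds. A primary objective stated in 10.1.1 has no analysis that can answer it, although the paired data are on the form. No figure in the plan is wrong; the gap is an omitted summary. Its consequence is that, with no reading above 44°C, the planned temperature result is 0/45 (upper limit 7.9%) or 0/50 (7.1%) for any amount of warming below the cut-off. A paired summary would locate the mean change to within about 0.3 SD at either sample size, assuming both readings are available for nearly all patients. The point should be fixed, but it does not threaten the adverse-event analysis or any stopping rule. The 44°C proportion is a reasonable safety summary and should stay.

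**What to change.** In protocol 10.1.1 and SAP 7.b:

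- Add, separately for the pre-surgery and post-surgery sessions, the within-patient change (post-imaging minus pre-imaging): number of patients with both readings, mean with 95% CI, median, and range including the maximum. Label it descriptive, since there is no control arm.
- Keep the above-44°C proportion as a second summary, state that the patient is the unit, and say which readings count.

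Two smaller items:

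- Reconcile the 44°C wording between 6.1.1 and SAP 2.a.i on one side and 10.1.1 and SAP 7.b on the other.
- State when the readings are taken relative to the skin cleaning and gel in Table 2 step 22, because Table 2 contains no temperature step.

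The analysis change costs a few sentences, a few lines of code and one more summary per session. It needs no new data or patients, because all four readings and their times are on Appendix A item 4. The timing statement is a small procedural addition. It cannot be applied to patients already scanned, because the form records when readings were taken but not when the skin was cleaned or gel applied.

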10.2 Analysis of Secondary Objective

10.2.1 There are three secondary outcomes of interest, two of these will be based upon a positivity (yes/no) (secondary outcomes 1 and 3) and one of these will assess on a continuous scale tumor size/ volume (secondary outcome 2). In each of these analyses, we will compare the information gathered from the MSOT approach (size, positivity tumor (yes/no), positivity of dye (yes/no)) for each patient and then compare these measures to those that are available from information gathered in the standard of care approach (i.e., from pathology reports after resection).

For continuous outcomes we will examine three characteristics based on comparing the MSOT and standard of care (“gold standard”) assessments. These include: 1) the mean difference in the measure (i.e., tumor volume or size), 2) the correlation between the measures taken using MSOT or standard of care; and 3) the comparison of variability of the measures from the two approaches (MSOT and standard of care). For the first approach we will calculate a paired t-test, for the second we will estimate a Pearson correlation and for the third we will perform an F-test to compare the equality of variances. With the expanded sample size of 50 patients we can detect a difference in values of volume (or size) equal to 0.4 standard deviations or less of the measure of difference in tumor volumes (or size) with 80% power using a paired t-test with $\alpha=0.05$ (2-sided). In addition, there is 80% power to detect a correlation of 0.38 (or larger) with an $\alpha=0.05$ (2-sided). Finally, there is 80% power to detect a ratio of 2.24 (or larger) when comparing variances between the two groups (note: this ratio corresponds to a ratio of 1.5 on the standard deviation scale).

If the study is terminated early with 45 patients scanned, we can still detect a difference in values of volume (or size) equal to 0.43 standard deviations or less of the measure of difference in tumor volumes (or size) with 80% power using a paired t-test with

alpha=0.05 (2-sided). In addition, there is 80% power to detect a correlation of 0.40 (or larger) with an alpha=0.05 (2-sided). Additionally, there is 80% power to detect a ratio of 2.35 (or larger) when comparing variances between the two groups (note: this ratio corresponds to a ratio of 1.53 on the standard deviation scale)

For binary outcomes (positivity and presence of dye), we will estimate the MSOT approach and the corresponding 95% Clopper-Pearson exact binomial confidence interval. Accuracy is defined as the number of patients where the MSOT and standard of care approach are in agreement (i.e., both are positive or both are negative). In addition, we can examine other characteristics of the two approaches including sensitivity, specificity, positive predictive value and negative predictive values.

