6.2 Secondary Outcomes

- 6.2.1 Tumor positivity as based on standard clinical laboratory techniques and signal detection of oxy- and deoxy-hemoglobin using MSOT localization
- 6.2.2 Tumor volumes as estimated by MSOT and by standard clinical laboratory techniques
- 6.2.3 Identification of tumor and/or lymph nodes based upon either Isosulfan Blue or IC Green dye

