7.0 Study Plan

7.1 Study-Related Activities

Study Procedures

- Upon receipt of a signed consent form, the research study team will generate a unique identification number so that subjects are de-identified for analysis of data. *Any standard imaging measurements will be added in [Appendix A and B](#).* This unique identification number will be used on the case report form ([Appendix A and B](#)).
- Patients will go through standard care procedures to prepare for surgery. Medically established diagnostic procedures will be used to detect tumor and lymph node margins.
- To evaluate the safety of MSOT ([Figure 2](#)), the device will be used to obtain images of the tumor or lymph node margins for investigational use only to compare to clinical pathology and patient's medical record.
- As part of the standard of care surgery preparation for cancer resection for all tumor types, patients will be injected with standard doses of Isosulfan Blue/ Indocyanine (IC) Green for either lymph node or tumor identification as part of the standard surgical procedure. The MSOT device will detect the presence of dye at the standard dose of dye used for surgical evaluation of tissue.

Figure 2 The MSOT Acuity

- Images will be obtained pre- and post-surgery (example simulation of operating room shown [Figure 3](#)). All imaging will be done in a closed surgical patient; no imaging will be performed on an open surgical patient. [name] has been trained in the use of the MSOT Acuity by the manufacturer, and she will be the MSOT operator for all MSOT imaging for this study. [name] will train the surgeon and surgical staff in the proper procedure for using the handheld

[figure not shown]
[figure not shown]
[figure not shown]
[figure not shown]
[figure not shown]
Figure 3: Demonstration of MSOT scanning procedure. A. Handheld detector covered with drape; B. surgeon; C. MSOT Acuity; D. trained MSOT operator.

detector and will maintain training records for this purpose. Only [name] and her research staff will perform post-imaging analysis on the de-identified digital images stored on the MSOT Acuity. The pathologist and clinician will perform all clinical evaluations of tumor samples as well as post-imaging assessment of treatment area and report where indicated on the imaging case report form. MSOT imaging will be for research only and no treatment decisions will be based on the MSOT images obtained.

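### Protocol 10.2 makes pathology reports the reference for dye positivity, but no pathology item or other form field records whether the target took up dye

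*Protocol*

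**What the plan says.** Protocol 6.2.3 defines the third secondary outcome as "Identification of tumor and/or lymph nodes based upon either Isosulfan Blue or IC Green dye". Section 7.1 gives the purpose of the dye: "patients will be injected with standard doses of Isosulfan Blue/ Indocyanine (IC) Green for either lymph node or tumor identification". It adds that the device detects whether dye is present.

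Section 10.2 sets one comparison for all three secondary outcomes: "In each of these analyses, we will compare the information gathered from the MSOT approach". Dye is named among the measures, "positivity of dye (yes/no)) for each patient and then compare these measures", and the plan is to "compare these measures to those that are available from information gathered in the standard of care approach (i.e., from pathology reports after resection". The analysis follows: "For binary outcomes (positivity and presence of dye), we will estimate the MSOT approach", with an exact 95% interval. Accuracy counts a patient as agreeing only when MSOT and standard of care are both positive or both negative. Sensitivity, specificity and the predictive values are mentioned as further options.

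On the forms:
- The pathology block of Appendix A (item 3) holds date of diagnosis, tumor tissue yes/no, TNM stage and subtype.
- Item 1e asks "Was an indicator dye used during surgery", and item 1f asks which dye.
- The dye fields in Appendix B are listed among the MSOT parameters.

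The SAP lists the dye endpoint in section 2.b. Its secondary analyses (7.c) cover only tumor positivity and oxygenation levels.

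**The concern.** The outcome is about localization: did MSOT find the dye, and so the tumor or node? The stated reference is about disease: does the tissue contain tumor? These answers differ whenever a dyed target is free of tumor. That can be foreseen here, because Appendix A allows a lymph node as the target and provides an N0 box.

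At stake is what the results for 6.2.3 mean. Scored against tumor status, they would largely describe how often dyed tissue contains tumor. There is also a practical risk: if dye uptake in the target is not written down at surgery, it may not be recoverable later. The primary safety analysis is not affected.

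**Working it through.** **Plan's own figure.** There is none to reproduce. The power statements in 10.2 concern tumor volume or size, and the interval bounds in 10.3 concern adverse events.

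**Step 1: what could serve as the yes/no reference for dye?**
- Item 3b (tumor tissue): yes/no and from pathology, but it is tumor status.
- Items 3c and 3d (TNM, subtype): not a dye result.
- Items 1e and 1f: whether a dye was used and which one, not whether the target took it up. They are also not pathology items.
- Appendix B dye fields: these are the MSOT reading itself.

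Only item 3b fits the comparator in 10.2.

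**Step 2: apply the agreement rule.** Suppose every target is dyed and MSOT detects dye perfectly.
- Target recorded tumor-positive: MSOT yes, reference yes, agreement.
- Target recorded tumor-free: MSOT yes, reference no, disagreement.

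Sensitivity is then 100% by construction. Specificity is 0% as soon as one target is tumor-free, although the device has made no error.

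**Step 3: size.** Neither input is in the documents, so both are assumptions: f is the share of targets that are nodes, and q is the share of those nodes recorded as tumor-free. Assume also that every non-node target is tumor-positive. Then agreement = 1 − f×q.

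| f | q = 50% | q = 90% |
|---|---|---|
| 30% | 1 − 0.15 = 85% | 1 − 0.27 = 73% |
| 50% | 1 − 0.25 = 75% | 1 − 0.45 = 55% |
| 100% | 1 − 0.50 = 50% | 1 − 0.90 = 10% |

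Item 3b appears once per form and is not tied to the node. If it is answered for the patient, a clean dyed node in a patient with confirmed tumor is recorded as positive. Agreement then moves towards 100%, but the reference has almost no negatives and still does not measure dye.

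**Step 4: imperfect detection.** Let p = 1 − f×q, and let d be the chance that MSOT shows the dye, independent of tumor status. Accuracy = p×d + (1 − p)×(1 − d). The coefficient of d is 2p − 1, so better detection lowers the score when p is below 50%. At p = 20% (for example f = 100%, q = 80%), d = 0.5, 0.7, 0.9 and 1.0 give 50%, 38%, 26% and 20%. This reversal does not occur in the f = 30% and f = 50% rows, where p is at least 55%.

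**Step 5: the same device against a dye reference.** With perfect detection, agreement is 50/50 = 100% (exact 95% interval 92.9 to 100), or 45/45 (92.1 to 100) if the study stops at 45.

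**The case against.** The strongest reply is that the protocol never states that dye is cross-tabulated with tumor status. Section 10.2 can be read as like with like: size with size, tumor with tumor, dye with dye. A pathology report might mention dye, or might confirm that the resected tissue is a node, in which case a dyed tumor-free node is a correct identification. Section 7.1 also speaks of comparison with the medical record, and 7.2 allows record review for up to 6 months. Finally, this is one secondary outcome in a safety study; no treatment decision and no sample size depends on it.

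Part of this stands. The mis-scoring follows from combining the comparator, the agreement rule and the form; it is not a sentence in the protocol. But the comparator in 10.2 is written as a definition, which narrows the medical-record route. No field captures a dye result or node confirmation from pathology, and SAP 7.c does not settle the matter.

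Two stronger readings are tempting and are not supported:
- A reader might infer that agreement will be only 10–50%. That needs every target to be a node with tumor status recorded for that node. Appendix A allows tumor targets, and every eligible patient has a solid tumor scheduled for removal.
- A reader might infer that undyed patients enter the comparison as MSOT-negative. Section 7.1 describes dye for all tumor types while item 1e allows a No, and those passages need reconciling. But nothing says how undyed patients are handled, and items 1e and 1f can identify them. The plan simply states no denominator.

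**Conclusion.** The concern holds in this form: the plan has no valid reference for dye. As written, the one yes/no comparison that the collected pathology data permit scores dye against tumor status, so accuracy, sensitivity and specificity for 6.2.3 would not measure dye or node identification.

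The size cannot be fixed from the documents. Under the assumptions in the working, a perfect device would show agreement anywhere from 10% to 85% over the values tabulated, and closer to 100% if tumor status is recorded for the patient. The low end belongs only to an all-node study and should not be quoted as the expected result. The point is worth correcting because the change is small, but it concerns a secondary outcome only.

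**What to change.** - In 10.2, name a dye-specific reference for 6.2.3: the surgeon's routine intra-operative observation of dye in the target (yes/no). Keep pathology as the reference for 6.2.1.
- Add one field for this to Appendix A beside item 1f. Table 2 has the surgeon holding the probe, so state that the field is completed without reference to the MSOT dye reading.
- State the denominator as patients with item 1e answered Yes.
- Add the matching analysis to SAP 7.c.

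The cost is one form field and a few sentences; the field records an observation and changes no care. The denominator may shrink, and few targets may be undyed among patients who received dye. The main result may therefore be a detection proportion with its Clopper-Pearson interval. Specificity and negative predictive value should be reported only if there are enough reference negatives.

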4.0 Patient Selection

4.1 Inclusion Criteria

- 4.1.1 Patients with an identified solid tumor, i.e. breast (Stage I-IV), melanoma (Stage I-IV), HNSCC (Stage I-III), pancreatic (Stage I-III), ovarian (Stage I-IV) that is scheduled for surgical removal of the tumor and completed standard imaging prior to surgery
- 4.1.2 Have acceptable hematologic status [total hemoglobin (tHb) \geq 10 mg/dL]
- 4.1.3 Patients \geq 18 yrs of age
- 4.1.4 Patient provided a signed and dated informed consent
- 4.1.5 Willing to comply with study procedures and be available for the duration of the study
- 4.1.6 Ability to understand and the willingness to sign an IRB-approved informed consent document.

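### Tumor volumes are compared untransformed with no safeguard against skew; if they are strongly skewed, a few large tumors dominate all three planned results, and a log-ratio analysis would be a cheap improvement

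*Protocol*

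**What the plan says.** Protocol 10.2.1 compares MSOT with pathology on tumor volume or size in three ways. The target of the first is "the mean difference in the measure (i.e., tumor volume or size"). The first two methods are given as: "For the first approach we will calculate a paired t-test, for the second we will estimate a Pearson correlation". The spread of the two methods is compared by a third procedure, an F-test of equal variances.

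For 50 patients it gives three effects detectable with 80% power: "With the expanded sample size of 50 patients we can detect a difference in values of volume (or size) equal to 0.4 standard deviations", a correlation of 0.38, and a variance ratio of 2.24. If the trial stops at 45 patients, these become 0.43 SD, 0.40 and 2.35.

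No transformation, rank-based alternative or check for skewness is named. The SAP repeats tumor volume among its objectives but lists no volume endpoint and no volume analysis. Its signed-rank test is for oxygenation levels only.

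Protocol 4.1.1 admits "breast (Stage I-IV), melanoma (Stage I-IV), HNSCC (Stage I-III), pancreatic (Stage I-III), ovarian (Stage I-IV"). The tumor form in Appendix A offers T categories from Tis to T4. No mean, SD or range of tumor volume appears in either document.

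**The concern.** Volume grows as the cube of diameter. A sphere of 1 cm diameter has volume π/6 × 1³ = 0.52 mL, and one of 5 cm has π/6 × 5³ = 65 mL, a 125-fold difference. Volumes pooled across five cancers and most stages could therefore be strongly right-skewed. If measurement error is roughly proportional to size, the raw differences will also have very unequal spread.

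All three planned procedures rest on sums of squares or cross-products, which large values dominate, and the stated detectable effects assume roughly normal data. Three things are at stake:
- A constant proportional bias in MSOT could be missed by the t-test.
- The Pearson correlation could depend on a handful of patients.
- The variance test could report a difference in spread that is not there.

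This question of scale is separate from whether the variance test allows for pairing.

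**Working it through.** **The plan's own figures.** Paired t-test: noncentral t with n−1 df. Correlation: Fisher z with SE 1/√(n−3). Variances: two-sided F for two independent groups of n.

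| | n=50: power at stated effect (effect for 80%) | n=45: power at stated effect (effect for 80%) |
|---|---|---|
| Paired t, 0.40 / 0.43 SD | 79.2% (0.404) | 80.5% (0.427) |
| Correlation, 0.38 / 0.40 | 78.3% (0.387) | 78.4% (0.407) |
| Variance ratio, 2.24 / 2.35 | 79.8% (2.245) | 80.0% (2.350) |

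All six are within 2 points of 80%, so the stated figures are correct under their normal-theory assumptions. What remains open is the scale.

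**Model (assumed).** True log volume is normal with SD s. Each method adds independent normal log error with SD σ. MSOT is shifted by ln(0.8). Because σ is the same for both methods, the ratio of arithmetic means is also 0.8, so the raw and log tests face the same bias. The range used is s = 1.0 to 1.5 and σ = 0.3 to 0.5, with n = 45.

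**What s means in diameters.** The 95% range of diameters has largest/smallest = exp(2 × 1.96 × s/3). This is 1.9-fold at s=0.5, 3.7-fold at s=1.0 and 7.1-fold at s=1.5.

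**Power on logs.** The standardized effect is |ln 0.8|/(σ√2).
- σ=0.3: 0.223/0.424 = 0.526; times √45 gives noncentrality 3.53; power 93%.
- σ=0.5: 0.223/0.707 = 0.316; times √45 gives 2.12; power 54%.

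These do not depend on s.

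**Power on raw volumes (simulation).** About 63% at s=1.0, σ=0.3, falling to about 16% at s=1.5, σ=0.5.

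**Type I error.** With no true difference, the raw t-test rejects about 3% to 4% of the time. It loses power, but its error rate is not inflated.

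**Variance tests with truly equal variances (nominal 5%).** Pitman-Morgan tests the correlation of (MSOT + pathology) with (MSOT − pathology), so it allows for pairing.

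| | Raw volume | Log volume |
|---|---|---|
| Planned F-test | 21% to 48% | 0% to 0.2% |
| Pitman-Morgan | 56% to 70% | 5% |

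Pairing alone does not cure the raw test, and logs alone do not cure the F-test. On logs the F-test ignores the positive correlation within patients and almost never rejects.

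**Influence (n=50, σ=0.3).** At s=1.0 and 1.5, the three largest contributions supply:
- 66% and 81% of the sum of squares of the differences;
- 65% and 78% of that of the volumes;
- 65% and 78% of the correlation cross-product.

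On logs each share is about 30%. At s=1.0, the 95% range of the sample Pearson r is 0.73 to 0.98 raw and 0.86 to 0.95 on logs.

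**Milder skew (n=50, σ=0.3, true ratio 1.2).** Raw t-test power is 80%, 74%, 51% and 30% at s = 0.3, 0.5, 1.0 and 1.5, against about 84% on logs throughout. The raw F-test still rejects 14% and 16% under equality at s = 0.3 and 0.5.

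**Zeros.** The log of zero is undefined. Dropping 1, 2, 5 or 10 of 50 patients moves the detectable difference from 0.404 SD to 0.408, 0.413, 0.427 or 0.454 SD. Adding a constant instead is unsafe: with 5 zeros of 50 and otherwise unbiased readings, constants from 0.01 to 1 give geometric ratios from 0.54 to 0.84.

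**The case against.** **The skewness is assumed.** A reader might infer that a few large tumors will decide all three results. The documents do not support this, because they give no volume distribution and T categories on a form are not one. Section 10.2.1 also allows size, and a linear diameter has one third of the log-SD of volume. When both methods carry error, the raw-diameter t-test comes close to the log version. This stands, and it makes the point conditional. Against it, s=0.5 would need nearly all tumors to lie within about a twofold range of diameters, which is narrow for this eligibility. A raw paired variance test on diameter still rejects about 12% to 26% of the time at diameter log-SD 0.3 to 0.5.

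**The log scale has a cost.** A reader might infer that it is free. It is not, because zeros are foreseeable: objective 3.2.3 includes MSOT volume after resection, 10.2.1 anticipates negatives by either method, and patients with neoadjuvant therapy are admitted. The question also changes from a mean difference to a geometric mean ratio, and the two can part. With error-free pathology, MSOT error 0.3 to 0.5, n=45 and no bias in the arithmetic mean, the log test rejects 16% to 38% of the time. This stands, and it is the reason to keep the raw mean difference as supporting output.

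**Near-certain power on logs.** Power above 99% for a 20% bias arises only if pathology has no measurement error. With error on both methods it is 54% to 93%.

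**Limited consequence.** This is a secondary outcome of a feasibility study that the SAP describes as mainly about safety, and MSOT images guide no treatment. That limits the weight of the point but does not remove it.

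**Conclusion.** The concern holds in conditional form. The volume comparison is planned on the raw scale with no protection against skew. If volumes have a log-SD of 1.0 to 1.5, a few large tumors dominate all three results: t-test power falls to about 16% to 63% where logs give 54% to 93%, and the F-test rejects about 21% to 48% of the time under equal variances. These figures rest on assumed lognormal volumes, log error SD of 0.3 to 0.5 on both methods, n=45 and, for power, a 20% geometric bias.

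The documents do not support reading this as an invalid t-test or as an error in the stated detectable effects. Nor would taking logs alone repair the variance comparison, which also needs a paired test. The point is a cheap improvement to a secondary analysis.

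**What to change.** In Protocol 10.2.1, and as an added volume endpoint and analysis in the SAP, prespecify the following for tumors with a positive volume (or diameter) by both methods:
- a paired t-test on log(MSOT/pathology), reported as a geometric mean ratio with 95% CI;
- the Pearson correlation on logs;
- a Pitman-Morgan test on logs in place of the F-test.

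Report zero or undetected volumes by either method as a separate count with the detection results, without adding a constant. Keep the raw mean difference as supporting output.

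State the detectable difference in SDs of the log ratio. The 0.40 and 0.43 SD figures and the correlations carry over for the same number of usable pairs. The variance ratios 2.24 and 2.35 assume independent groups, so they must be restated for a paired test with an assumed correlation.

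The cost is a short passage in each document and no change in sample size. The estimate becomes a ratio conditional on detection by both methods, and tumors that MSOT missed leave the agreement estimate, so the detection count must be read beside it.
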